## 9.6 Evaluation of Safety

---

Analyses will be performed for all patients having received at least one dose of study drug. The study will use the NCI CTCAE v4.0. Safety and tolerability will be assessed by incidence, severity, and changes from baseline of all relevant parameters including AEs, laboratory values, and vital signs.

AEs will be coded using the latest available version of the Medical Dictionary for Regulatory Activities (MedDRA). AEs will be summarized for each treatment arm by the number and percentage of patients who experienced the event, according to system organ class (SOC) and preferred term (PT). Additional summaries will also be provided by severity grade and relationship to study drug, and for SAEs and events resulting in the permanent discontinuation of therapy. A subject reporting multiple cases of the same AE will be counted once within each SOC and similarly counted once within each PT, and AEs will be graded by worst severity grade. Unless specified otherwise, the denominator for these calculations will be based on the number of patients in each treatment arm who receive at least one dose of study drug, irrespective of the total number of doses administered.

Vital sign results (systolic and diastolic blood pressure, pulse, respiration, and body temperature) will be summarized descriptively for each scheduled and unscheduled protocol time point. Changes will be calculated relative to the assessments at baseline.

The changes in hematology, chemistry, and other laboratory values will be summarized descriptively for each scheduled and unscheduled protocol assessment time point. Changes will be calculated relative to the values collected at baseline. Data listings of all laboratory data collected during the study will be presented. Laboratory values outside normal limits will be identified in data listings and will include flags for high and low values.

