##### **Secondary objectives**

- 1) To assess overall and progression-free survival distributions (Arms 1, 2 & 3).
- 2) To assess the objective response rate to treatment (Arms 1, 2 & 3).
- 3) To further delineate the safety profile of the combination of everolimus and TMZ (Arm 2)
- 4) To assess whether treatment (Arms 1, 2 & 3) provides clinical benefit by reducing seizure frequency

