**Secondary Endpoints (for all arms):**

- 1) Median and distribution of overall survival (OS) and PFS
- 2) Objective Response Rate (ORR)
- 3) Number of adverse events related to combination treatment
- 4) Rate of Reduction in Seizures (as outlined in van den Bent, Wefel *et al.* 2011)

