#### **4 Study design**

Treatment for patients with previously untreated LGG will be selected by whether or not their tumor has ATRX loss and/or 1p/19q chromosomal co-deletion. If the tumor is ATRX lost or 1p/19q intact, then patients will be further selected by whether or not their tumor demonstrates activation of the PI3K/mTOR pathway. If activation is present, patients will be treated in Arm 1 with single-agent everolimus at 10 mg daily continuously. If activation is not present, patients will be treated in Arm 2 with combined everolimus and TMZ. Everolimus will be given at 10 mg daily continuously, and TMZ will be dosed initially at 150 mg/m^2/day for 5 days out of a 28-day cycle. If ATRX is intact, 1p/19q co-deletion should be confirmed, or if only 1p/19q co-deletion is available and present, patients will be treated in Arm 3 with single-agent everolimus at 10 mg daily continuously. In all arms, treatment with everolimus will continue for up to 24 cycles, after which patients will be followed with interval MRIs until progression. In Arm 2, TMZ will be stopped after 12 cycles.

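### The Arm 2 adverse-event tables do not separate time on both drugs from time on one drug, so they give an upper limit on toxicity during the combination but do not isolate it

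*Combined protocol and SAP*

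**What the plan says.** Section 3 sets secondary objective 3: "To further delineate the safety profile of the combination of everolimus and TMZ (Arm 2"). The matching secondary endpoint is "Number of adverse events related to combination treatment".

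Section 4 gives the two drugs different durations. "In all arms, treatment with everolimus will continue for up to 24 cycles", but "In Arm 2, TMZ will be stopped after 12 cycles". The end of section 6.2.2 lets Arm 2 patients stay on TMZ when everolimus is stopped for toxicity. The end of section 6.2.3 lets them stay on everolimus when TMZ is stopped.

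Section 9.6 holds the only analysis that bears on endpoint 3; section 9.5.3 does not mention it. The main rule is "AEs will be summarized for each treatment arm by the number and percentage of patients who experienced the event". Counting is per patient: "A subject reporting multiple cases of the same AE will be counted once within each SOC and similarly counted once within each PT", at worst grade. The denominator is the patients in each arm "who receive at least one dose of study drug, irrespective of the total number of doses administered". The section also promises that "Additional summaries will also be provided by severity grade and relationship to study drug". Under section 8.2 the investigator attributes each event to the investigational drug on a five-level scale, with no separate entry for each drug or for the combination.

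Vital signs and laboratory values, by contrast, are summarised in section 9.6 at each protocol time point.

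**The concern.** Being in Arm 2 is not the same as being on the combination. Up to 12 of the 24 planned cycles are everolimus alone, and early stops can add further single-drug time. A first event of a given type in cycle 20, on everolimus alone, enters the Arm 2 percentage in the same way as one in cycle 2 on both drugs.

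The summary by relationship does not separate them, because an everolimus-related event in cycle 20 is still related to study drug. Elsewhere the protocol does treat the phases as different: section 7.1.2 sets a different blood-count schedule for Arm 2 on both drugs and on everolimus alone, and section 6.2.1 presumes different toxicities for each drug.

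At stake is how the Arm 2 percentages are read. Quoted as the toxicity of the combination, they may be too high by an amount that the planned tables do not reveal.

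**Working it through.** **The plan's own figures.** No numerical target is stated for the safety objective. The one design figure for Arm 2 is the 86% in section 9.3 (35 patients, 50% against 70%, one-sided 10%). It reproduces: declaring success at 22 or more of 35 gives an exact binomial type I error of 0.088 and power of 0.865. It does not depend on the point made here.

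**Inputs from the documents.** Both drugs for 12 cycles and everolimus for up to 24 (section 4); 35 patients in Arm 2 (section 5). The planned share of cycles on both drugs is 12/24 = 50%.

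**Direction.** Each patient is counted once per term over a fixed denominator. Adding single-drug time can only leave the count unchanged or raise it. With the same denominator, the pooled percentage is therefore an upper limit on the percentage during the combination. The two are equal only if no patient has a first event of that type outside the combination period.

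**Size, under assumptions.** The documents give no adverse-event rates by phase. Let p12 be the proportion with the event in cycles 1-12, and k the ratio of the hazard on everolimus alone to the hazard on both drugs. Assume that the hazard is constant within each phase, that every patient completes 24 cycles, and that there is no carry-over. Then

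P(event by cycle 24) = 1 - (1 - p12)^(1 + k).

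For p12 = 0.20 and k = 0.5: 1 - 0.80^1.5 = 0.284.

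| p12 (assumed) | k = 0 | k = 0.25 | k = 0.5 | k = 1 |
|---|---|---|---|---|
| 10% | 10.0% | 12.3% | 14.6% | 19.0% |
| 20% | 20.0% | 24.3% | 28.4% | 36.0% |
| 30% | 30.0% | 36.0% | 41.4% | 51.0% |
| 40% | 40.0% | 47.2% | 53.5% | 64.0% |

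At p12 = 20% in 35 patients, 7.0 expected patients on the combination become 8.5, 10.0 or 12.6 in the pooled table for k = 0.25, 0.5 or 1. Across the four rows, the share of counted patients whose first event falls in cycles 13-24 is 0% at k = 0, 15-19% at k = 0.25, 25-32% at k = 0.5 and 38-47% at k = 1.

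**The direction depends on the measure.** With events per patient-cycle, counting all events over full exposure, pooling would dilute the rate instead. The ratio of pooled to on-combination rate is (12 + 12k)/24, that is 0.5, 0.625, 0.75 and 1.0 for k = 0, 0.25, 0.5 and 1. Section 9.6 plans no such rate, so the upper-limit statement applies to the percentages that it does plan.

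**The case against.** Arm 2 is defined as everolimus for up to 24 cycles with TMZ for the first 12, and objective 3 names that arm. A by-arm table over all treated patients is a valid description of that regimen and contains every event that occurs on both drugs. This stands. A reader might infer that the plan fails to measure the combination's safety at all; it does not isolate it, which is a smaller fault.

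Laboratory values and vital signs are reported by time point and can be read by nominal phase. This also stands, and it limits the point to the adverse-event tables.

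A reader might also infer that pooling is what prevents Arms 1 and 3 from showing what TMZ adds. The documents do not support that. All arms have the same planned everolimus duration, so whole-period tables are balanced on planned everolimus time. The obstacle is that arms are assigned by tumour biomarkers and not by randomisation, and section 9.6 plans no between-arm safety comparison. Nor does the heading that lists the secondary endpoints for all arms carry much weight, since objective 3 already limits the item to Arm 2.

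The illustration rests on assumed hazards and full treatment. Section 6.2.2 describes everolimus events as mostly reversible and not building up over time. Progression and early stops would shorten the later phase. The excess could therefore be small.

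Finally, counting only events on both drugs would lose late effects of TMZ; section 2.2 itself mentions treatment-related leukaemia with alkylating agents. This is a sound reason to add a table and not to replace the existing one.

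**Conclusion.** The point holds for the adverse-event tables. They describe the whole Arm 2 regimen and give an upper limit, not an estimate, for the percentage of patients with an event during the combination. Neither the summary by relationship nor any other planned adverse-event table separates the periods.

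The direction follows from the counting rule and needs no assumed rates. The size is unknown. The 24-36% against 20% is illustrative only and depends on the assumed 20% incidence, constant hazards, full treatment and k between 0.25 and 1; at k = 0 there is no excess. The primary endpoint, the sample size and the toxicity stopping rule in section 9.4 do not use these tables. This is a reporting gap in a descriptive secondary objective, worth closing because the repair is cheap.

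**What to change.** In section 9.6:

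- Keep the arm-level table as it stands.
- Add an Arm 2 adverse-event table by actual exposure, not by cycle number. The on-combination period runs from the first day on both drugs to the permanent stop of either drug, plus a pre-stated lag, for example 30 days. The lag must be added to the stop date. A rule that took the earlier of the TMZ stop and 30 days after its last dose would never apply the lag, and would book delayed events to everolimus alone.
- Show single-drug time separately, including late events.
- In each period give the number and percentage of patients with the event, and events per patient-cycle.

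In section 3, state endpoint 3 for Arm 2 only, as patients with related adverse events in the on-combination period, reported alongside the whole-period figure. This also removes the mismatch between an endpoint that counts events and an analysis that counts patients. Label any display beside Arms 1 and 3 as descriptive.

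The cost is a short change of wording, one derived period flag and a few more tables. Doses and dose changes are already recorded (sections 6.1.1 and 7.1.2). Adverse-event onset dates are presumed to be collected but are not expressly listed, so this should be confirmed. Treatment, visits and sample size do not change.

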## **10 Study Management**

### **10.1 Pre-study Documentation**

This study will be conducted in accordance with the ethical principles that have their origin in the Declaration of Helsinki as stated in 21 CFR §312.120(c)(4); consistent with GCP and all applicable regulatory requirements.

Before initiating this trial, the Investigator will have written and dated approval from the Institutional Review Board for the protocol, written informed consent form, subject recruitment materials, and any other written information to be provided to subjects before any protocol related procedures are performed on any subjects.

The clinical investigation will not begin until either FDA has determined that the study under the Investigational Drug Application (IND) is allowed to proceed or the Investigator has received a letter from FDA stating that the study is exempt from IND requirements.

The Investigator must comply with the applicable regulations in Title 21 of the Code of Federal Regulations (21 CFR §50, §54, and §312), GCP/ICH guidelines, and all applicable

---

regulatory requirements. The IRB must comply with the regulations in 21 CFR §56 and applicable regulatory requirements.

## **10.2 Institutional Review Board Approval**

The protocol, the proposed informed consent form, and all forms of participant information related to the study (e.g. advertisements used to recruit participants) will be reviewed and approved by the UCSF CHR (UCSF Institutional Review Board). Prior to obtaining CHR approval, the protocol must be approved by the Helen Diller Family Comprehensive Cancer Center Site Committee and by the Protocol Review Committee (PRC). The initial protocol and all protocol amendments must be approved by the IRB prior to implementation.

## **10.3 Informed Consent**

All participants must be provided a consent form describing the study with sufficient information for each participant to make an informed decision regarding their participation. Participants must sign the CHR-approved informed consent form prior to participation in any study specific procedure. The participant must receive a copy of the signed and dated consent document. The original signed copy of the consent document must be retained in the medical record or research file.

## **10.4 Protocol amendments, or changes in study conduct**

Any change or addition (excluding administrative) to this protocol requires a written protocol amendment that must be reviewed by Novartis and the investigator before implementation. Amendments significantly affecting the safety of subjects, the scope of the investigation or the scientific quality of the study require additional approval by the IRB at each study center. A copy of the written approval of the IRB must be provided to Novartis. Examples of amendments requiring such approval are:

- increases in drug dose or duration of exposure of subjects,
- significant changes in the study design (e.g. addition or deletion of a control group),
- increases in the number of invasive procedures,
- addition or deletions of a test procedure required for monitoring of safety.

These requirements for approval should in no way prevent any immediate action from being taken by the investigator or by Novartis in the interests of preserving the safety of all patients included in the trial. If an immediate change to the protocol is felt to be necessary by the investigator and is implemented for safety reasons Novartis must be notified and the IRB at the center must be informed immediately. Amendments affecting only administrative aspects of the study do not require formal protocol amendments or IRB approval but the IRB must be kept informed of such administrative changes. Examples of administrative changes not requiring formal protocol amendments and IRB approval include:

1. changes in the staff used to monitor trials
2. minor changes in the packaging or labeling of study drug.

## **10.5 Handling and Documentation of Clinical Supplies**

The UCSF Principal Investigator will maintain complete records showing the receipt, dispensation, return, or other disposition of all investigational drugs. The date, quantity and batch or code number of the drug, and the identification of patients to whom study drug has been dispensed by patient number and initials will be included. The sponsor-investigator will maintain written records of any disposition of the study drug.

The Principal Investigator shall not make the investigational drug available to any individuals other than to qualified study patients. Furthermore, the Principal Investigator will not allow the investigational drug to be used in any manner other than that specified in this protocol.

## **10.6 Case Report Forms (CRFs)**

The Principal Investigator and/or his/her designee, will prepare and maintain adequate and accurate participant case histories with observations and data pertinent to the study. Study specific Case Report Forms (CRFs) will document safety and treatment outcomes for safety monitoring and data analysis. All study data will be entered into OnCore® via standardized CRFs in accordance with the CTMS study calendar, using single data entry with a secure access account. The Clinical Research Coordinator (CRC) will complete the CRFs as soon as possible upon completion of the study visit; the Investigator will review and approve the completed CRFs.

The information collected on CRFs shall be identical to that appearing in original source documents. Source documents will be found in the patient's medical records maintained by UCSF personnel. All source documentation should be kept in separate research folders for each patient.

In accordance with federal regulations, the Investigator is responsible for the accuracy and authenticity of all clinical and laboratory data entered onto CRFs. The PI will approve all completed CRFs to attest that the information contained on the CRFs is true and accurate.

All source documentation and CTMS data will be available for review/monitoring by the UCSF DSMC and regulatory agencies.

The Principal Investigator will be responsible for ensuring the accurate capture of study data. At study completion, when the CRFs have been declared to be complete and accurate, the database will be locked. Any changes to the data entered into the CRFs after that time can only be made by joint written agreement among the Study Chair, the Trial Statistician, and the Protocol Project Manager.

## **10.7 Oversight and Monitoring Plan**

The UCSF Helen Diller Family Comprehensive Cancer Center DSMC will be the monitoring entity for this study. The UCSF DSMC will monitor the study in accordance with the NCI-approved Data and Safety Monitoring Plan (DSMP). The DSMC will routinely review all adverse events and suspected adverse reactions considered "serious". The DSMC will audit

---

study-related activities to ensure that the study is conducted in accordance with the protocol, local standard operating procedures, FDA regulations, and Good Clinical Practice (GCP). Significant results of the DSMC audit will be communicated to the IRB and the appropriate regulatory authorities at the time of continuing review, or in an expedited fashion, as applicable. See Appendix 3, Data and Safety Monitoring Plan for a Phase 2 or 3 Institutional Study, for additional information.

## **11 Protection of Human Subjects**

### **11.1 Protection from Unnecessary Harm**

Each clinical site is responsible for protecting all subjects involved in human experimentation. This is accomplished through the CHR mechanism and the process of informed consent. The CHR reviews all proposed studies involving human experimentation and ensures that the subject's rights and welfare are protected and that the potential benefits and/or the importance of the knowledge to be gained outweigh the risks to the individual. The CHR also reviews the informed consent document associated with each study in order to ensure that the consent document accurately and clearly communicates the nature of the research to be done and its associated risks and benefits.

### **11.2 Protection of Privacy**

Patients will be informed of the extent to which their confidential health information generated from this study may be used for research purposes. Following this discussion, they will be asked to sign the HIPAA form and informed consent documents. The original signed document will become part of the patient's medical records, and each patient will receive a copy of the signed document. The use and disclosure of protected health information will be limited to the individuals described in the informed consent document.

## 13 Appendices

### Appendix 1: Karnofsky Performance Scale

Percent	Description
100	Normal, no complaints, no evidence of disease
90	Able to carry on normal activity; minor signs or symptoms of disease
80	Normal activity with effort; some signs or symptoms of disease
70	Cares for self, unable to carry on normal activity or to do active work
60	Requires occasional assistance, but is able to care for most of his/her needs
50	Requires considerable assistance and frequent medical care
40	Disabled, requires special care and assistance
30	Severely disabled, hospitalization indicated Death not imminent
20	Very sick, hospitalization indicated Death not imminent
10	Moribund, fatal processes progressing rapidly
0	Dead

## Appendix 2: Molecular Assays

### Section A: Immunohistochemical Assays

All antigens to be assayed in this protocol will be scored using a semi-quantitative scale as described herein:

The designated neuro-pathologists will identify areas on the glass slide that are appropriately stained with the antibody, and will review the positive and negative control samples. The neuropathologist will then determine the ratio of tumor cells staining positive to those staining negative for the particular antibody. This interpretation does not consider intensity of staining per cell, but defines as “positive” all cells staining in a similar fashion to positive control cells. Based on this interpretation, the results are categorized into four groups:

- 0- Negative staining = no staining of the tumor cells
- 1- Focal positive staining = staining similar to positive control in less than or equal to 33% of the tumor cells;
- 2- Intermediate positive staining = staining similar to positive control in positive staining in greater than 33% but less than or equal to 66% of the tumor cells;
- 3- Diffuse positive staining = staining similar to positive control in greater than 66% of the tumor cells.

Visual estimation may be aided by dividing the interpretable areas of the tissue on the slide into four quadrants using a tissue marker. It is beneficial to provide a visual scale in the form of a figure for the initial publications that will utilize the grading system. The results of this scoring can be reported as either a number representing each category, or descriptively using the terms negative, focal, intermediate, and diffuse.

All tumor tissues will be analyzed to assess both 1p/19q chromosomal status and activation of PI3K/Akt/mTOR signaling. 1p/19q chromosomal status will be performed and interpreted in a laboratory which is CAP accredited and CLIA certified to perform high complexity testing. The 1p/19q Deletion by FISH assay is designed to identify chromosomal deletions involving the 1p36 and 19q13 regions. It utilizes two Vysis(TM) dual-color DNA probe sets. Probe set one includes the loci-specific identifier (LSI) 1p36 that hybridizes to the 1p target on chromosome 1, producing an orange signal while LSI 1q25 serves as a reference probe for 1q, producing a green signal. Likewise, probe set two includes LSI 19q13 that hybridizes to the 19q target on chromosome 19, producing an orange signal, and a 19p reference probe LSI 19p13 that produces a green signal. Formalin-fixed, paraffin-embedded tissue on two glass slides is de-paraffinized and then treated with pepsin to digest tissue proteins and allow for probes to reach target DNA. The DNA is then heat denatured and subsequently allowed to hybridize with the two probe sets, one per slide. After hybridization, the slides are washed to remove any of the excess unbound probes and the nuclei are counterstained with DAPI (4,6 diamidino-2-phenylidole). Enumeration of 1p, 1q, 19p and 19q signals is conducted by

microscopic examination of cell nuclei using a fluorescence microscope equipped with appropriate excitation and emission filters. An adjacent H&E stained section of the case is reviewed to evaluate tumor and normal tissue morphology and to identify the appropriate area of FISH analysis.

In addition, all tumors will be molecularly profiled based on known alterations in adult LGGs. First, tumors will be divided into one of two categories, PI3K/AKT/mTOR activated (Pathact) or non-activated (Pathnon-act), based upon the results of immunohistochemistry (IHC) for p-PRAS40 as described below. Second, all tumor samples will be further characterized by IHC, tumor-DNA sequencing, and FISH, for additional molecular aberrations, as described below.

PI3K/AKT/mTOR activated tumors (Pathact) will be those with a score of 1 or higher for phosphorylated PRAS40. We will analyze expression and phosphorylation of other proteins in the pathway by IHC with antibodies listed in the Table above and score them as described in detail above. Additional immunohistochemical assays will include IHC to determine p53 expression, Ki67 expression as determined by MIB-1, IDH1R132H, and ATRX.

